4.1 Rationale for study design

This 1-year extension study will provide additional safety data for two doses of iscalimab (600 mg and 300 mg). This study will also provide continued administration of iscalimab for participants that as per Investigator may potentially derive clinical benefit after completing the core study. The extension study will provide additional key safety data for the two doses of iscalimab to better understand the overall safety of iscalimab and potentially inform study design elements of subsequent clinical studies (i.e., Phase III). The study will allow for the assessment of continued evaluation of efficacy and tolerability. Furthermore, digital data collected as part of the extension study will build on existing digital data for further validation.

A follow-up period of 12 weeks (14 weeks after the last dose) is required to reach sub-pharmacological exposures after completion of dosing and was estimated taking into consideration the non-linear pharmacokinetics (target-mediated disposition) of iscalimab - see [Section 4.2](#) below for detailed PK considerations.

The study is blinded until the final database lock of the core study to protect the integrity of the data in the ongoing core study. Participants can exit the study upon their own wish or based on advice of the Investigator at any time.

4.1.1 Rationale for choice of background therapy

[figure not shown]
Local remedies for symptom relief and systemic background medication as per local practice is allowed, as long as participants are on stable dose (Section 6.2.1) and in accordance with the inclusion/exclusion criteria.

4.2 Rationale for dose/regimen and duration of treatment

CFZ533 (iscalimab) 600 mg or 300 mg will be administered s.c., weekly for the first 3 doses (Weeks 60E1, 61 and 62); then, from Week 64, iscalimab will be administered s.c. bi-weekly (every other week or Q2W). This is illustrated in Figure 4-1 for Arm 1 (iscalimab 600 mg maintenance regimen) and Arm 2 (iscalimab 300 mg maintenance regimen).

- For participants assigned to the iscalimab 600 mg maintenance regimen (Arm 1), the loading doses are 600 mg on Week 60E1, 61 and 62, followed by a bi-weekly maintenance regimen at 600 mg.
- For participants assigned to the iscalimab 300 mg maintenance regimen (Arm 2), the loading doses are 600 mg on Week 60E1, and 300 mg on Week 61 and Week 62, followed by a bi-weekly maintenance regimen at 300 mg.

Figure 4-1 Iscalimab doses and regimen

^a 600 mg s.c.: 2 injections of 2 mL iscalimab (300 mg/2 mL); ^b 300 mg s.c.: 1 injection of 2 mL iscalimab (300 mg/2 mL) and 1 injection of 2 mL placebo; ^c every other week (bi-weekly) s.c. administration

Rationale for the loading doses

Iscalimab is subject to CD40-mediated elimination (or target-mediated drug disposition (TMDD)), and the level of expression of CD40 receptors in target tissues has the potential to affect exposure to iscalimab, and ultimately target engagement. High CD40 expression may be associated with high elimination rate of iscalimab and loss of CD40-CD154 (CD40 ligand) pathway blockade if CD40 receptors are not fully saturated.

The proposed loading regimen is aiming to rapidly achieve the CD40 receptor saturation and minimal CD40-mediated elimination, in conditions where CD40 expression might be enhanced and additionally also to rapidly establish close to steady-state conditions for iscalimab concentration in plasma.

The 3 weekly loading doses of iscalimab in SjS patients are guided by PK data collected in the proof-of-concept (PoC) Study CCFZ533X2203 in pSS. Based on these results the loading and further maintenance regimen will rapidly provide and sustain the systemic exposures above the threshold of 40 µg/mL for a broad population. This threshold was associated with complete suppression of germinal center development in cortical B cell areas of lymph nodes and T cell dependent antibody response in non-human primates (NHP).

As demonstrated in the PoC Study CCFZ533X2203 in pSS, a single s.c. dose of 600 mg iscalimab at Day 1 will deliver plasma concentrations generally above 40 µg/mL after 1 week. Subsequent weekly doses on Week 61 and 62 in Arms 1 and 2 are expected (i) to maintain CFZ533 plasma levels above 40 µg/mL, and (ii) to deliver iscalimab trough levels that are close to expected steady state conditions.

Further supportive arguments on the selected loading dosing regimen are provided in the Rationale for dose/regimen and duration of treatment of the TWINSS core study protocol (refer to Section 4 of the core study protocol).

Rationale for maintenance regimen

The maintenance regimen of 600 mg s.c. Q2W is expected to provide a median steady state trough plasma level at about 144 µg/mL (90% of the population within 282 - 46 µg/mL), in the upper range of trough levels observed in the PoC Study CCFZ533X2203-Cohort 2 (i.v. regimen; these concentrations were associated with clinical efficacy and suppression of a biologically relevant biomarker CXCL13 - a marker of germinal center activity).

The maintenance regimen of 300 mg s.c. Q2W is expected to deliver a median steady state trough plasma level at about 54 µg/mL (90% of the population within 125 - 0.1 µg/mL), with a reasonable chance to show efficacy in SjS.

The between subject variability in exposure within the two treatment arms (to a lesser extent in the 600 mg treatment arm) is likely to depend on the biology of CD40 in target tissues (expression level, turnover) and its potential modulation during the treatment period.

Rationale for the duration of the safety follow-up period (target engagement after the last dose)

Based on predicted median CFZ533 plasma concentration-time profile at 600 mg s.c. Q2W regimen, at about 14 weeks after the last dose, iscalimab plasma concentrations are expected to drop below 20 µg/mL with no expected pharmacodynamic activity in target tissues (e.g., germinal centers; data from non-human primates - please see current IB).

A 12-week follow-up period (14 weeks after the last dose) has been selected for the study and is justified to monitor for any related serious adverse events (SAE).

4.3 Rationale for choice of control drugs (comparator/placebo) or combination drugs

There is no placebo or active control group in this study given the purpose and main objectives are to extend treatment of participants who completed the core study. The use of two different doses of iscalimab (iscalimab 600 mg and 300 mg) will allow evaluation of both doses in terms of safety, tolerability and sustainability of clinical benefits. Placebo injection will be provided

to maintain blinding until the final database lock of the core study to protect the integrity of the data in the ongoing core study. For more details refer to [Section 6.1.1](#).

4.4 Purpose and timing of interim analyses/design adaptations

There is no interim analysis planned for the study. The final analysis of the study will be performed at the end of the study. The end of the study is defined when all re-assigned participants have completed Week 120 or discontinued earlier. The extension study may be amended if deemed necessary based on the results of the TWINSS core study Week 24 primary analysis.

4.5 Risks and benefits

The risk to participants in this trial may be minimized by compliance with the eligibility criteria (refer to [Section 5](#)) and study procedures, as well as close clinical monitoring.

Risks:

The potential safety concerns in humans and the investigator guidance related to administration of CFZ533 are based on the data from the available clinical trials with CFZ533, preclinical and toxicological data, as well as experience with other compounds of the same class.

In the indication of SjS there are no identified risks beyond those described in detail in Section 7 of the current edition of the CFZ533 IB. Important Potential Risks for CFZ533 are summarized in [Table 4-1](#) below:

Table 4-1 Potential risks associated with CFZ53

Risk 1 Infections

Participants treated with CFZ533 may be at an increased risk of infection. CD40 ligation is linked to the functional activity of antigen presentation, as well as T-cell priming, B-cell differentiation, antibody production and immune memory. Administration of CFZ533 is expected to result in general immunosuppression with a decreased capacity to mount a response to novel immunogens, including those of bacterial, viral, fungal and parasitic origin when full receptor occupancy has been achieved.

Although the ability to mount a primary immune response will be affected by CFZ533, the memory B-cell repertoire should remain intact and protective. In addition, participants will have adequate preformed antibody to maintain protective humoral response for extended periods of time (months). The participants will be monitored during the study for any signs and symptoms of infections including serology tests for cytomegalovirus (CMV; human-cytomegalovirus) infection.

Risk 2 Malignancy including Lymphoproliferative disorder

With immunosuppression there is a risk of developing lymphoproliferative disorders. Of note, lymphomas are also known to occur more frequently in participants with pSS as compared to the age- and sex-matched control population. No signs of lymphoproliferative disorders have been observed in NHP studies, or in clinical trials in healthy volunteers or participants where CFZ533 was evaluated.

Hematology will be regularly monitored for changes consistent with a lymphoproliferative disorder. A physical examination will be performed to check for unusual lymphadenopathy in the absence of infection.

Risk 3 Thrombophilia/ Thrombosis

There is a hypothetical risk for thromboembolic complications when targeting this co-stimulatory pathway. This risk is based on clinical results from previous compounds (e.g. BG9588, IDEC-131) which have targeted CD154 (CD40 ligand) and resulted in a fatal hyper-coagulation phenotype.

Although the risk is theoretical, hematologic and coagulation parameters will be monitored in the current study. Furthermore, participants with conditions such as antiphospholipid syndrome, who are at a higher risk for thromboembolism, will be excluded unless they are receiving antithrombotic prophylaxis. CFZ533 binds to CD40 receptor and is Fc-silent mAb hence does not appear to carry the same risk of thrombosis. Both preclinical and clinical data from an extensive Phase 2 clinical program across healthy subjects and participants across different indications have not indicated a risk of thrombosis with CFZ533.

Risk 4 Immunogenicity

As with any monoclonal antibody, there is a hypothetical risk of developing anti-CFZ533 antibodies. However, it is likely that CFZ533 doses will achieve complete receptor occupancy during the treatment period. In these conditions, it is expected that CFZ533 will retain its capacity to block immune responses, including those directed against the drug itself, neutralizing or not.

Samples will be collected during study to assess immunogenicity. Immunogenicity will be monitored during clinical development and the consequences of an immune response to CFZ533 could be correlated with, a loss of exposure (PK), a loss of peripheral CD40 receptor occupancy (PD), and/or the appearance of immune related adverse events including injection site reactions.

Risk 5 Vaccination Failure

Vaccination of participants during treatment with CFZ533 and prior to clearance of the antibody is likely to result in therapeutic failure (i.e., non-protective antibody titers) due to the pharmacologic activity of the antibody. Administration of live attenuated vaccines should be avoided while receiving CFZ533 treatment and for at least 14 weeks thereafter.

One fatal event (potential CMV infection) was reported in the CCFZ533X2202 clinical trial in Lupus nephritis, suspected to be related to the study medication by the Investigator.

The event was confounded by CMV infection present before first administration of the study medication, low lymphocyte count at baseline and concomitant immunosuppressive medications like MMF and prednisolone. The ultimate cause of death remains unclear; however, the events leading to fatal outcome could have been associated with the CMV infection and/or with a bacterial superinfection, and a role of study drug cannot be excluded.

Currently, the causal effect of CFZ533 remains unclear, however, active viral infections do remain a potential risk. Specific detection measures have been implemented to monitor the risk of CMV infection across the clinical development program for CFZ533.

The infections including CMV are considered as an important potential risk for CFZ533 and will continue to be closely monitored and mitigated in the current study.

Lastly, women of childbearing potential (WOCBP) must be informed that taking the study treatment may involve unknown risks to the fetus if pregnancy were to occur during the study. In order to participate in the study, they must adhere to the contraception requirements outlined in the exclusion criteria. If there is any question that the participant will not reliably comply, they should not be entered or continue in the study.

For further information on the above specific risks and other potential adverse effects of the compound please refer to Section 7 of the current edition of the CFZ533 IB.

Benefits:

The study design allows that all participants are treated with standard treatment for SjS, including systemic treatments such as hydroxychloroquine or immunosuppressive medicines where indicated, as long as the dose is kept stable ([Section 6.2.1](#)) and the potential risks and benefits from these medicines are known. Based on the preliminary safety and efficacy data from the exploratory PoC study of iscalimab in pSS, it is possible that a number of participants in one or both iscalimab dose arms experience clinically important benefit from iscalimab treatment in the current study.

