4.6 Rationale for Public Health Emergency mitigation procedures

During a Public Health emergency as declared by Local or Regional authorities i.e. pandemic, epidemic or natural disaster, mitigation procedures to ensure participant safety and trial integrity are listed in relevant sections. Notification of the Public health emergency should be discussed with Novartis prior to implementation of mitigation procedures, and permitted/approved by Local or Regional Health Authorities and Ethics Committees as appropriate.

5 Study Population

The study population will consist of male and female participants ≥ 18 years, with SjS defined according to the American College of Rheumatology/European League Against Rheumatism (ACR/EULAR) 2016 classification criteria ([Shiboski et al 2017](#)) who have completed the entire treatment period up to Week 48 and the mandatory 12 weeks follow-up period up to Week 60 of the TWINSS core study. The study population has previously been described in detail in the core study protocol (refer to Section 5 of the core study protocol). Enrollment will be determined by the number of participants completing the core study. It is estimated that approximately 160 participants may choose to enter the extension study from the core study.

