5.1 Inclusion criteria

Participants eligible for inclusion in this study must meet **all** of the following criteria:

1. Participants must have participated in the TWINSS core study, CCFZ533B2201, and must have completed the entire treatment period up to Week 48 and the follow-up period up to Week 60
2. Signed informed consent must be obtained prior to participation in the extension study (i.e. before commencement of the Week 60 assessments of the core study)
3. In the judgement of the Investigator, participants must be expected to clinically benefit from continued iscalimab therapy

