 - Male sterilization (at least 6 months prior to screening and confirmed as successful). For female patients in the study, the vasectomized male partner should be the sole partner for that patient. In case the vasectomized male partner is not the sole partner of the female patient, highly effective method of contraception must be applied (double barrier contraception is not sufficient)
 - Use of oral, (estrogen and progesterone), injected or implanted hormonal methods of contraception or placement of an intrauterine device (IUD) or intrauterine system (IUS) or other forms of hormonal contraception that have comparable efficacy (failure rate < 1%), for example hormone vaginal ring or transdermal hormone contraception. In case of use of oral contraception women should have been stable on the same pill for a minimum of 3 months before taking investigational drug

Women are considered post-menopausal and not of child bearing potential if they have had 12 months of natural (spontaneous) amenorrhea with an appropriate clinical profile (e.g., age appropriate, history of vasomotor symptoms) or have had surgical bilateral oophorectomy (with or without hysterectomy), total hysterectomy or tubal ligation at least

six weeks ago. In the case of oophorectomy alone, only when the reproductive status of the woman has been confirmed by follow up hormone level assessment she is considered not of childbearing potential.

In case local regulations deviate from the contraception methods listed above, local regulations apply and will be described in the Informed Consent Form (ICF).

6. Missing ESSDAI (Cohort 1 and Cohort 2) or ESSPRI (Cohort 2) scores in the core study at Weeks 0 and 4 or Weeks 40 and 48.

6 Treatment

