6.1.3 Treatment arms/group

No re-randomization is planned for the extension study. The treatment re-assignment for the extension study occurs at visit Week 60E1 which is the last visit of the core study (Week 60). Upon completion of the core study, Investigators will use their clinical judgment including responder definitions provided below to decide if it is beneficial for participants to continue with the extension study based upon response to therapy at the end of the treatment period of the core study.

Participants will be re-assigned to one of the following two treatment arms:

- Arm 1 - Iscalimab 600 mg s.c. Q2W
- Arm 2 - Iscalimab 300 mg s.c. Q2W

At Week 60 of the TWINSS core study, all eligible participants from the core study can opt to be enrolled in the extension study via IRT. The Week 60E1 visit will be performed on the same day once the Week 60 visit of the core study is completed by the participant. The Investigator or his/her delegate will contact the IRT after confirming that the participant fulfills all the extension study inclusion/exclusion criteria. An IRT algorithm will be programmed to assign the participant to blinded treatment in the extension study using ESSDAI (Cohort 1 and Cohort 2) and ESSPRI (Cohort 2) assessment scores from predefined time points in the TWINSS core study.

- For participants rolling over from Cohort 1 in the TWINSS core study, the change in ESSDAI score between Week 4 and Week 48 will be used to determine if the participant responded to treatment in the core study. If an ESSDAI score is missing at Week 4 and/or Week 48, then Week 0 or Week 40 scores should be respectively used for the algorithm. A decrease of 3 points or more from Week 4 (or Week 0 if the ESSDAI score is missing at Week 4) will classify the participant as a treatment responder in Cohort 1.

- For participants rolling over from Cohort 2 in the TWINSS core study, a change in both ESSDAI and ESSPRI scores between Week 4 and Week 48 will be used to determine if the participant responded to treatment in the core study. If an ESSDAI or ESSPRI score is missing at Week 4 and/or Week 48, then Week 0 or Week 40 scores should be respectively used for the algorithm. A decrease of 1 point or more in both the ESSDAI and ESSPRI scores from Week 4 (or Week 0 if the ESSDAI or ESSPRI score is missing at Week 4) will classify the participant as a treatment responder in Cohort 2.

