6.2.1 Concomitant therapy

All medications, procedures, and significant non-drug therapies (including physical therapy and blood transfusions) administered after the participant was enrolled into the study must be recorded on the appropriate Case Report Forms.

Each concomitant drug must be individually assessed against all exclusion criteria/prohibited medication. If in doubt, the Investigator should contact the Novartis medical monitor before re-assigning treatment for a participant or allowing a new medication to be started. If the participant is already enrolled, contact Novartis to determine if the participant should continue participation in the study.

Concomitant treatment may include standard of care for dry eye and dry mouth symptoms, such as the use of artificial tears and artificial saliva/salivary stimulants (e.g., cevimeline, pilocarpine) at the discretion of the treating physician. Amount and frequency of use should be recorded at each visit.

Short term use of oral analgesics (NSAIDs, paracetamol) is permitted. Azathioprine (up to 150 mg/day), methotrexate (≤ 25 mg/week) and hydroxychloroquine (≤ 400 mg/day) are allowed as stable background medication defined as continued treatment ≥ 3 months without dose adjustments. Steroids (prednisone or equivalent ≤ 10 mg/day) are allowed during the extension study and tapering is permitted at intervals not exceeding prednisone 2.5 mg/2 weeks.

Pre-emptive therapy with lamivudine or entecavir is allowed for participants with Hepatitis B surface antigen (HBsAg) seroreversion while on study treatment. Similarly, CMV antiviral medication used as pre-emptive therapy is allowed for participants with detectable virus by PCR.

Note: Background and concomitant medications will not be provided by Novartis and must be supplied by the study center.

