6.7.2 Instruction for prescribing and taking study treatment

All kits of study treatment assigned by the IRT will be recorded in the IRT system.

Study treatment (iscalimab 600 mg and 300 mg) will be administered s.c. by the participant, caregiver or site staff. The PFS will be provided by the site staff to the participant, who will self-administer the injections at the specified study time point. Participants will be instructed in detail how to self-administer the s.c. injection using the PFS. Site staff will administer the injection to those participants who are not able or unwilling to self-administer the PFS injection. Detailed instructions on the self-administration of the study treatment will be described in the IFU and provided to each participant. It shall be recorded on the corresponding eCRF(s) whether the participant self-administered the PFS or whether site staff or caregiver administered the PFS and whether it was administered at home or at the site.

Iscalimab 600 mg s.c. Q2W

- Iscalimab loading doses will be 600 mg s.c. (2 injections of 300 mg/2 mL) on Week 60E1 (Day 421), Week 61 (Day 428) and Week 62 (Day 435)
- From Week 62 the participant will receive 600 mg s.c. Q2W iscalimab until Week 106 (last dose)

Iscalimab 300 mg s.c. Q2W

- Iscalimab loading doses will be 600 mg s.c. (2 injections of 300 mg/2 mL) on Week 60E1 (Day 421), 300 mg s.c. (1 injection of 300mg/2 mL and 1 injection of 2 mL of the placebo) on Week 61 (Day 428) and 300 mg s.c. Week 62 (Day 435)
- From Week 62 the participant will receive 300 mg s.c. Q2W iscalimab until Week 106 (last dose)

The first study treatment administration will occur at Week 60E1 after the inclusion/exclusion criteria have been confirmed, all study scheduled assessments have been performed and the scheduled blood samples have been drawn. For the loading doses on Week 60E1 (Day 421), Week 61 (Day 428) and Week 62 (Day 435), all injections will be self-administered by the participant at the study site under the supervision of a site staff member after the study assessments for the visit have been completed. Participants will be required to attend the study site for the Week 64 visit and starting at Week 66, the participants will be allowed to self-administer the study medication at home on an alternating basis through to Week 106 or continue to present at the study site for injection administrations, based on the participant's preference and the investigator's judgment.

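### Protocol 4.5 says antiphospholipid syndrome without antithrombotic prophylaxis is excluded, but the eligibility criteria in 5.1 and 5.2, confirmed before the first extension dose, do not contain this

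*Protocol*

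**What the plan says.** Protocol 4.5 opens with eligibility as one of its means of risk control: "The risk to participants in this trial may be minimized by compliance with the eligibility criteria". It refers to Section 5 for those criteria and adds study procedures and close monitoring. Table 4-1, Risk 3 (thrombophilia/thrombosis), first promises hematologic and coagulation monitoring in the present study. It then states that "participants with conditions such as antiphospholipid syndrome, who are at a higher risk for thromboembolism, will be excluded unless they are receiving antithrombotic prophylaxis".

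Section 5.1 lists three inclusion criteria: completion of the core study, consent, and the investigator's expectation of benefit ("In the judgement of the Investigator, participants must be expected to clinically benefit from continued iscalimab therapy"). Section 5.2 lists six exclusion criteria: overlap syndromes, other investigational drugs, infection, pregnancy or nursing, inadequate contraception, and missing disease scores ("Missing ESSDAI (Cohort 1 and Cohort 2) or ESSPRI (Cohort 2) scores in the core study").

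These lists control entry. Under 6.1.3 the investigator contacts the IRT "after confirming that the participant fulfills all the extension study inclusion/exclusion criteria". Under 6.7.2, "The first study treatment administration will occur at Week 60E1 after the inclusion/exclusion criteria have been confirmed".

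Two places point back to the core study. Section 5 says "The study population has previously been described in detail in the core study protocol". Footnote 10 of Table 8-1, repeated under the blood log in 16.5, limits on-treatment coagulation monitoring to participants with antiphospholipid antibodies and/or pre-existing antithrombotic treatment, and links that group to the core protocol's exclusion criteria.

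**The concern.** Section 4.5 announces a safety exclusion and refers to Section 5, and Section 5 does not contain it. An investigator who works through the Section 5 list at Week 60E1 is not prompted to ask whether a participant with antiphospholipid syndrome is still on prophylaxis. Section 11.3 requires monitors to verify adherence to the inclusion and exclusion criteria in full, so an item missing from those lists also falls outside that check.

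At stake is whether someone whom 4.5 says will be excluded could be given the loading doses again and scheduled for a further 48 weeks of treatment. This is a matter of safety consistency. It does not bear on any estimate or comparison.

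**Working it through.** There is no plan figure to reproduce. The check compares texts, with three small pieces of arithmetic.

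**1. Is the restriction anywhere in the entry criteria?** 3 (5.1) + 6 (5.2) = 9 criteria. The number naming antiphospholipid syndrome, thromboembolic risk or antithrombotic prophylaxis is 0. The nearest item is the last bullet of exclusion 1. It needs another connective tissue disease that is active, requires immunosuppression beyond the trial's scope and interferes with organ-domain scoring. It does not ask about prophylaxis.

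**2. Does 4.5 normally carry its exclusions into Section 5?** In the one comparable case it does. The fetal-risk paragraph of 4.5 refers to the exclusion criteria, and criteria 4 and 5 of Section 5.2 supply them. Risk 3 has no counterpart.

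**3. Does other text close the gap?**

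| Place | What it does | What it leaves open |
|---|---|---|
| Section 5, reference to the core protocol | Describes the population | Does not require core criteria to be met again |
| 6.2.1: "Each concomitant drug must be individually assessed against all exclusion criteria/prohibited medication" | Reviews drugs being taken | Does not detect a prophylactic that was stopped |
| Table 6-2 | Lists prohibited drugs | Does not list required ones |
| Table 8-1, footnote 10 | Selects who has on-treatment coagulation monitoring | Monitoring is not an entry condition |
| Blood log (16.5) | 1.8 mL coagulation sample at Weeks 60E1, 72, 84, 96 and 108 | No result is tied to eligibility |
| 9.1.1 | Requires stopping in any safety-risk situation | A general stopping rule, not an entry check |

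**4. Who is left?** All participants passed core entry. The remaining case is therefore a participant with such a condition who is unprotected at Week 60E1 because prophylaxis lapsed, or because the condition was diagnosed after core entry and not treated. A newly diagnosed participant who is already on prophylaxis is allowed by 4.5 and is not part of the point.

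**5. How old is the core entry check?** Week 60E1 is 60 weeks after core baseline. Core screening lasts 6 weeks, so the check is between 60 and 60 + 6 = 66 weeks old. This dates the entry check only; it does not show that no later check was made.

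**6. How much treatment would follow?** Weeks 60E1, 61 and 62 give 3 administrations. Weeks 64 to 106 every two weeks give (106 − 64)/2 + 1 = 22. The total is 3 + 22 = 25, which agrees with the 25 administration visits in Protocol Section 3.

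**The case against.** The strongest reply is that the core study has largely dealt with this. Only core completers can enter, footnote 10 links the restriction to the core exclusion criteria, and the Risk 3 sentence may simply be text carried over from the wider programme. The restriction also does appear in the extension protocol, and under 13.2 investigators sign to follow all of that protocol's instructions. Antibody-positive participants stay in the coagulation-monitored group whether or not they take prophylaxis, because footnote 10 reads and/or. The blood log lists a Week 60E1 coagulation sample, and the footnote's limit is worded for the on-treatment phase, so it may not restrict that first sample. Risk 3 itself calls the hazard theoretical and reports no thrombosis signal for CFZ533.

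All of this stands, and it makes the point small. A reader might infer that the extension abandoned the exclusion, or that unprotected patients were admitted. The documents support neither. The exclusion is written in 4.5, the core study is said to have applied it, and nothing shows that any such participant exists.

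The reply does not remove the mismatch. The sentence in 4.5 directly follows one about the present study, and the lists confirmed before assignment and dosing leave the condition out. Screening at core entry cannot detect what changed afterwards.

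**Conclusion.** The inconsistency is confirmed: 0 of 9 written criteria carry the exclusion that 4.5 states. Its practical reach is limited to participants who became unprotected after core entry. The documents give no basis for a count; it is probably very small.

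This is a minor correction for safety consistency. No endpoint, analysis set or summary changes. The textual finding is firm. The safety consequence is less certain, because the core protocol is not among the documents and a later core-study check cannot be ruled out. The Week 60E1 column of Table 8-1 is also not visible, so nothing is claimed about that visit beyond the coagulation sample in the blood log.

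**What to change.** Add one exclusion to 5.2: antiphospholipid syndrome, or another condition that the investigator judges to carry a raised risk of thromboembolism, unless antithrombotic prophylaxis is being received at Week 60E1. Leaving the second part to the investigator's judgement avoids an undefined list. It can be confirmed from the medical history and concomitant medication already collected.

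A Week 60E1 criterion cannot act on the 206 participants whom SAP 1.1 reports as enrolled. For them, make one review of the same records while dosing continues. For any unprotected case, start or resume prophylaxis where clinically appropriate, which satisfies 4.5. Otherwise stop study treatment under 9.1.1. If dosing has ended, the review still shows whether the commitment in 4.5 was kept.

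If the sponsor meant screening at core entry only, a sentence in 4.5 saying so would remove the conflict instead.

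Cost: one records check, one line through a protocol amendment with the approvals that 14.1 requires, and possibly a few exclusions or discontinuations. No new sample or test is needed.
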